5.3 Inclusion of Women, Minorities and Children

Both men and women and members of all races and ethnic groups are eligible for this study. Children are not eligible for this study because the safety and tolerability of the proposed dosing schedule has not been determined in adults.

5.4 Withdrawal Criteria

Protocol therapy will be discontinued at any time if any of the following situations occur:

1. Progressive disease (not including unconfirmed radiographic PD if Investigator opts to continue treatment as outlined in Section 8.2).
2. Adverse event.
 - The development of toxicity which, in the Investigator's judgment, precludes further therapy.
 - Unacceptable adverse event(s).
 - Intercurrent illness that prevents further administration of treatment.
3. Withdrawal by subject.
4. Lost to follow-up.
5. Non-compliance.
6. At the discretion of the Investigator/physician decision.
7. Death.
8. Pregnancy.
9. Study termination.

5.4.1 Withdrawn Subjects

When a patient is removed from the study, the Investigator will clearly document the reason in the medical record and complete the appropriate case report form describing the reason for discontinuation. In addition, every effort should be made to complete the appropriate assessments listed in Section 7.4.

Patients lost to follow-up will be withdrawn from the study. Patients will be declared "lost to follow-up" if the last contact date has exceeded two years, and/or the site has documented three attempts to contact the patient by telephone and/or certified letter to last known address.

5.4.2 Replacement of Subjects

Patients who discontinue due to toxicity (related to study drug) during the 4-week DLT window of observation of Cycle 1 and Cycle 2, or who do not receive all doses due to toxicity in Cycle 1 and Cycle 2, will not be replaced. Patients who discontinue or who do not receive at least two combination doses of HS-130/HS-110 for any reason other than toxicity during Cycle 1 and 2 will be replaced. Note, that all patients who enrolled in the study will be included in assessment of DLT per Section 6.1.2.

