6.1.1 Dose Escalation Scheme

Escalating doses of the viable, replication-incompetent, human whole cell vaccines, HS-130 and HS-110 will be administered to patients via intradermal injections/re-injections (up to 10 total) on Day 1 of a two-

week cycle. The length of each cycle is two weeks, and the DLT window of observation includes the safety data obtained from the first two treatment cycles, Cycle 1 and Cycle 2 (4 weeks).

Seven dose levels will be explored, and patients will receive separate escalating doses of HS-130 and HS-110 in alternating fixed 1:1 or 2:1 ratio based on the amount of secreted OX40L-Ig (HS-130) and gp96-Ig fusion protein (HS-110) per cell of the drug product. The starting dose of HS-130/HS-110 combination is based on the dose-ranging studies conducted in animal models of T cell expansion and tumor challenge, as well as established clinical experience from HS-110.

Table 2: HS-130/HS-110 Dose Levels

Cohort	Dose level	HS-130 dose* (ng/24-hr OX40L-Ig)	HS-110 dose* (ng/24-hr gp96-Ig)	HS-130: HS-110 Ratio	Total number of AD100 cells (Q2W) [#]	Minimum number of patients
1	-1	75 ng/24-hr	75 ng/24-hr	1:1	1.0 million	1
	1	150 ng/24-hr	150 ng/24-hr	1:1	1.9 million	1
	2	300 ng/24-hr	150 ng/24-hr	2:1	2.3 million	1
	3	300 ng/24-hr	300 ng/24-hr	1:1	3.8 million	1
	4	600 ng/24-hr	300 ng/24-hr	2:1	4.7 million	1
2	5	600 ng/24-hr	600 ng/24-hr	1:1	7.6 million	3
3	6	1,200 ng/24-hr	600 ng/24-hr	2:1	9.3 million	3
4	7	1,200 ng/24-hr	1,200 ng/24-hr	1:1	15.1 million	3

*The number of cells administered to achieve the HS-130 (ng/24-hr of OX40L-Ig protein) and HS-110 (ng/24-hr of gp96-Ig protein) dose will be determined based on the specifications for that batch of the drug product. For HS-130: Lot HBI-HS-130-FP-001 = 241 fg/cell/24-hr and HS-110: Lot 0000748931 = 104 fg/cell/24-hr. The productivity per cell will be determined using the same assay format and standards for pre-clinical and clinical derived material.

[#] The suggested total number of allogeneic tumor cells (AD100) administered every second week at the highest dose level is similar to or less than the weekly dose of 10 million HS-110 cells that has been established safe and immunologically effective in the HS-110 study (NCT02439450, IND No. 14814).

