The first cohort will employ an accelerated design to evaluate the first 4 dose levels in single patients. There will be a staggered enrollment with a minimum 1-week delay between each patient in cohort 1. If any drug-related \geq Grade 2 (other than Grade 2 injection site reaction with pain) event occurs during the first cycle of treatment, the study will revert to 3+3 design starting at that dose level.

Subsequent cohorts in the dose escalation phase will enroll patients following the standard 3+3 design. Three patients will be enrolled in each subsequent dose cohort and enrolled with a (minimum) 1-week staggered delay (i.e. Patient 2 to be dosed \geq 1-week after Patient 1 received the first dose, and Patient 3 to be dosed \geq 1-week after Patient 2 received the first dose).

In the 3-patient cohorts (i.e. 3 patients treated at the same dose), if 1 out of 3 patients experience a DLT during the first two treatment cycles, the dose cohort will be expanded up to 6 patients. If \geq 2 out of 6 patients experience DLTs, the MTD has been exceeded, and dose escalation will cease. Up to 3 additional patients will be enrolled at the next lowest dose if only 3 patients were treated at that dose level, to confirm safety of that dose. If a DLT is observed already with the first patient in Cohort 1, the Safety Review

Committee (Section 8.1.2.8.1) may suggest and approve a dose de-escalation cohort with at least 50 % reduction of HS-110 and HS-130 (dose level -1).

Once all patients in a cohort have completed the first two cycles of dosing and received at least 2 doses of HS-130/HS-110, the safety and tolerability of the combination treatment administered will be reviewed by the safety review committee (SRC). If 0 out of 3 patients or 1 out of 6 patients experience a DLT, then the SRC may recommend enrollment at the next higher dose level.

Any patient who does not receive two doses of the study treatment during the DLT window of observation (first 2 cycles/4 weeks), for reasons other than study drug-related toxicity and did not experience a DLT will not be taken into account in the assessment of the overall DLT rate for the particular dose level cohort and will be replaced.

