6.2 Dose Interruptions/Withholding

Study drug may be withheld from a patient based on the Investigator's decision in the event of intercurrent illness, adverse event, administrative reasons, or other reasons. If the patient's condition subsequently improves, or the situation that resulted in withholding study drug rectifies itself, the Investigator may resume dosing as soon as possible, unless the delay is more than 2-weeks. Doses should not be skipped.

Dosing should be delayed for any DLT-equivalent toxicity and possible >Grade 2 adverse events considered related to study medication. At the Investigator's discretion, dosing may recommence when the toxicity has resolved to Grade 2 or less. Immune related reactions or allergy should resolve to Grade 1 or less.

Treatment will be discontinued if the next cycle cannot be initiated if a TEAE has not resolved (to acceptable grade) after ≤ 2 weeks.

Patients who miss a dose during Cycle 1 and Cycle 2 may be replaced in the study per Section 5.4.2. The interruption and/or missed dose(s) should be recorded.

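### A patient who receives dose 2 and then leaves the study before day 28 is replaced under Section 5.4.2 but stays in the DLT denominator under Section 6.1.1

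*Combined protocol and SAP*

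**What the plan says.** - **Section 5.4.2 (Replacement of Subjects)** has two alternative triggers for replacement in Cycles 1 and 2: "Patients who discontinue or who do not receive at least two combination doses of HS-130/HS-110 for any reason other than toxicity". Either discontinuing or falling short of two doses is enough. The section then adds: "Note, that all patients who enrolled in the study will be included in assessment of DLT per Section 6.1.2".
- **Section 6.1.1 (Dose Escalation Scheme)**, and the same rule in the synopsis, has one trigger: "Any patient who does not receive two doses of the study treatment during the DLT window of observation". If the shortfall arose "for reasons other than study drug-related toxicity and did not experience a DLT will not be taken into account in the assessment" of the DLT rate, the patient is replaced. A patient who received two doses does not meet this condition.
- **Section 6.2 (Dose Interruptions/Withholding)** makes replacement optional: "Patients who miss a dose during Cycle 1 and Cycle 2 may be replaced in the study per Section 5.4.2".
- **The window**: Section 6.1.1 says the "DLT window of observation includes the safety data obtained from the first two treatment cycles, Cycle 1 and Cycle 2 (4 weeks"). Dose 2 is given on Cycle 2 Day 1, with a visit window of 2 days either way (Section 7.3.2.1).
- **Use of the count**: escalation follows 0 of 3 or 1 of 6 patients with a DLT (Section 6.1.1). The MTD needs at least 6 evaluable patients (Section 6.1.3), but no section says who is evaluable for DLT. Section 9.1 defines only a safety and an efficacy population.

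**The concern.** The two replacement rules give different denominators for the same patient. Cohorts have 3 or 6 patients, so the classification of one patient can decide whether the dose goes up. If Section 6.1.1 is followed as written, a patient who had dose 2 and then left the study contributes a DLT-free result based on little more than half the observation period. That lowers the apparent DLT rate and favours escalation, in a first-in-human trial whose Section 2.3.2 reports no formal GLP toxicology studies for HS-130. The case is foreseeable, because Section 5.4 lists withdrawal, loss to follow-up and death among the reasons for stopping. Without one rule, the choice would be made cohort by cohort after the data are known.

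**Working it through.** **Step 1. Apply each rule to the same patient.** The patient receives both doses, has no DLT, and leaves the study between dose 2 and day 28 for a non-toxicity reason.

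| Source | Trigger | Result |
|---|---|---|
| 5.4.2 | discontinues, or fewer than two doses | replaced |
| 6.1.1 and synopsis | fewer than two doses | not excluded, not replaced; stays in the denominator without a DLT |
| 6.2 | missed dose | does not apply |

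**Step 2. Unobserved time.** Dose 2 falls on day 15 (range 13 to 17) of 28. A patient who leaves just after it has 28 - 15 = 13 days unobserved (range 11 to 15), about half the window.

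**Step 3. Effect on a cohort that contains one such patient.** The documents give neither a DLT rate nor its timing, so both are assumed. Let p be the true DLT probability over the window and s the share of that risk after dose 2. The early leaver then shows a DLT with probability q = p(1 - s). The cohort passes with 0/3, or with 1/3 followed by 0 of the next 3.

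- Replaced by a fully observed patient: P(pass) = (1-p)³ + 3p(1-p)² × (1-p)³
- Kept: P(0/3) = (1-p)²(1-q); P(1/3) = 2p(1-p)(1-q) + (1-p)²q; P(pass) = P(0/3) + P(1/3) × (1-p)³

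For p = 0.33 and s = 0.5, q = 0.165:

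- Replaced: 0.301 + 0.444 × 0.301 = 0.434
- Kept: P(0/3) = 0.449 × 0.835 = 0.375; P(1/3) = 0.442 × 0.835 + 0.449 × 0.165 = 0.443; P(pass) = 0.375 + 0.443 × 0.301 = 0.508

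With s = 0.25 or 0.75, the kept value is 0.471 or 0.545. As a check on the model, a constant-hazard form with half the window observed uses q = 1 - (1-p)^0.5.

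| p | Replaced | Kept, s = 0.5 | Kept, constant hazard |
|---|---|---|---|
| 0.10 | 0.906 | 0.924 | 0.923 |
| 0.20 | 0.709 | 0.756 | 0.754 |
| 0.33 | 0.434 | 0.508 | 0.501 |
| 0.40 | 0.309 | 0.386 | 0.377 |
| 0.50 | 0.172 | 0.242 | 0.230 |

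**Step 4. Average over the chance of having such a patient.** If 5% to 10% of patients leave unobserved in this interval (assumed), a cohort of three contains at least one with probability 1 - 0.95³ = 0.143 to 1 - 0.90³ = 0.271. At p = 0.33 the difference is 0.508 - 0.434 = 0.074, so the average effect is 0.074 × 0.143 = 0.011 to 0.074 × 0.271 = 0.020. At p = 0.10 it is 0.018 × 0.143 = 0.003 to 0.018 × 0.271 = 0.005. This counts one leaver per affected cohort and ignores leavers among the second three patients.

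**The case against.** **The rules can be read together.** Section 6.1.1 is silent on a two-dose early leaver and nowhere says that such a patient counts as DLT-free. Section 6.2 defers to 5.4.2, so one could replace on either trigger. Safety Review Committee review also waits until all patients have completed two cycles of dosing, and the committee may ask for more patients. This is a possible reading, but the review sentence governs timing and gives no replacement rule. The patient's place in the count follows from 6.1.1 having a single ground for exclusion.

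**Under 5.4.2 the patient may be replaced and still counted**, because of its all-enrolled note. This stands, and it means that the comparison of 0.43 with 0.51 takes replacement to be a swap. If it is not a swap, the denominator becomes 4, for which the 3+3 rule has no entry.

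**Most patients who stop are still observed.** Section 7.4 sets a safety visit 30 days after the last dose (about day 45) for all who discontinue treatment, Section 5.4.1 asks for every effort to complete it, and Section 8.1.2.7 covers SAEs to 30 days. This stands. A reader might infer that every patient who stops after dose 2 biases the DLT rate, but the documents do not support that. The bias needs loss of observation, as with consent withdrawal, loss to follow-up or unrelated death.

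**Other differences could be read as equally serious conflicts.** A reader might infer that 5.4.2 and 6.1.1 clash outright on unrelated toxicity, since one says toxicity and the other study drug-related toxicity. However, 5.4.2 opens with the related-to-study-drug qualifier, so the later use may simply not repeat it. A reader might also infer that 5.4.2, having no DLT exception, lets a DLT drop out when the patient is replaced. Its all-enrolled note keeps the DLT, and only the denominator is unclear.

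**Conclusion.** The contradiction between 5.4.2 and 6.1.1 (with the synopsis) is real for a patient who leaves the study after dose 2 and before day 28, and nothing elsewhere settles it. It concerns the count that decides escalation and the MTD, so it should be corrected. Cohorts 2 to 4 are affected, and any level in cohort 1 that reverts to 3+3.

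Its size is modest. For a cohort with one wholly unobserved leaver, the pass probability rises by about 7 percentage points at p = 0.33 (0.43 to 0.51, or 0.47 to 0.55 as the share of risk after dose 2 goes from 25% to 75%) and by about 2 points at p = 0.10. A reader might take the 7 points as the expected bias per cohort. It is conditional on such a patient being present, and the average is about 1-2 points at p = 0.33. The DLT rate, the split of risk and the leaver rate are all assumptions, but the conflict in the text does not depend on them.

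The *toxicity* qualifier, *may* in 6.2 against *will* in 5.4.2 and 6.1.1, and the missing DLT exception in 5.4.2 are lesser wording differences to resolve in the same edit.

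**What to change.** Reconcile the synopsis and Sections 5.4.2, 6.1.1 and 6.2 through one definition of a DLT-evaluable patient, stated once and cross-referenced:

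- A patient is evaluable if a DLT occurred at any time in the window, or if two doses were received and safety was observed to the end of the window. Follow-up after stopping treatment counts as observation.
- Every other patient is non-evaluable and replaced, except where dose 2 was missed because of study-drug-related toxicity.
- A patient with a DLT always stays in the count.
- Use the study-drug-related qualifier and *will be replaced* in every place, and align the all-enrolled note in 5.4.2 with the definition so that the denominator is clear. Let the evaluable patients in Section 6.1.3 refer to the same definition.

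The cost is a wording change in a few places and an occasional extra replacement patient when someone leaves after dose 2 and cannot be followed to day 28.

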5.5 Study Stopping Criteria

If any of the following occur, administration of HS-130/HS-110 will be temporarily or permanently stopped, pending a review by the Safety Review Committee. During that time, no drug can be administered to any patient, until a decision is made.

- Any Death (other than progressive disease) that is at least possibly related to the study agent(s)
- Occurrence of two or more grade 4 events that are at least possibly related to the study agent(s)

Conditions that may warrant trial termination are listed in Section 4.5.

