Adverse events will be assessed per CTCAE version 5. Any toxicity that is at least possibly related to the study drug may be considered as a DLT, which is defined as non-acceptable (as defined below) treatment related toxicity (i.e., not attributable to the active disease, disease-related processes under investigation or intercurrent illness) observed during the first 4 weeks (or Cycle 1 and Cycle 2) of study treatment. Ongoing safety events beyond Cycle 2 will be reviewed across all cohorts during the study to help inform dose escalation decisions. Note, that all patients who enrolled in the study will be included in assessment of DLT.

DLT is defined as non-acceptable toxicity which includes:

1. Hematological toxicities \geq Grade 3.
2. Non-hematological toxicity \geq Grade 3.
3. Autoimmunity \geq Grade 3
4. Any other toxicity (greater than at baseline), considered clinically significant and/or unacceptable, and that does not respond to supportive care and results in a disruption of the dosing schedule of more than 14 days.

DLT excludes:

1. Hematological and non-hematological \leq Grade 2 unless considered non-acceptable.
2. Grade 3 self-limited or medically controllable toxicities (e.g., fever without \geq Grade 3 neutropenia, nausea, vomiting, diarrhea, fatigue).
3. Electrolyte disturbances that are managed to Grade 1 or less with supplemental therapy.

A DLT will be considered related to HS-130/HS-110 treatment unless there is a clear, well-documented, alternative explanation for the AE. AEs that meet the above criteria but occur after the DLT window of observation will not be defined as DLTs, but will be reported as AEs/Serious Adverse Events (SAEs), as applicable, and will be reviewed across all cohorts during the study to help inform dose escalation decisions.

In case of suspicion of a DLT, the Investigator must inform the Medical Monitor/Sponsor immediately. The DLT will be confirmed by the Medical Monitor/Sponsor and a decision must be taken by the Sponsor regarding if an *ad hoc* SRC meeting is required.

Patients who are tolerating HS-130/HS-110 will not have to discontinue dosing prematurely due to the occurrence of DLTs in another patient in the same cohort, unless decided by the SRC. If requested by the Investigator, depending on the nature of the DLT and patient status, the SRC and the Sponsor may allow a patient to continue with study treatment at a reduced dose.

Safety Review Committee (SRC)

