6.1.2 Dose-Limiting Toxicity

Adverse events will be assessed per CTCAE version 5. Any toxicity that is at least possibly related to the study drug may be considered as a DLT, which is defined as non-acceptable (as defined below) treatment related toxicity (i.e., not attributable to the active disease, disease-related processes under investigation or intercurrent illness) observed during the first 4 weeks (or Cycle 1 and Cycle 2) of study treatment. Ongoing safety events beyond Cycle 2 will be reviewed across all cohorts during the study to help inform dose escalation decisions. Note, that all patients who enrolled in the study will be included in assessment of DLT.

DLT is defined as non-acceptable toxicity which includes:

1. Hematological toxicities \geq Grade 3.
2. Non-hematological toxicity \geq Grade 3.
3. Autoimmunity \geq Grade 3
4. Any other toxicity (greater than at baseline), considered clinically significant and/or unacceptable, and that does not respond to supportive care and results in a disruption of the dosing schedule of more than 14 days.

DLT excludes:

1. Hematological and non-hematological \leq Grade 2 unless considered non-acceptable.
2. Grade 3 self-limited or medically controllable toxicities (e.g., fever without \geq Grade 3 neutropenia, nausea, vomiting, diarrhea, fatigue).
3. Electrolyte disturbances that are managed to Grade 1 or less with supplemental therapy.

A DLT will be considered related to HS-130/HS-110 treatment unless there is a clear, well-documented, alternative explanation for the AE. AEs that meet the above criteria, but occur after the DLT window of observation will not be defined as DLTs, but will be reported as AEs/Serious Adverse Events (SAEs), as applicable, and will be reviewed across all cohorts during the study to help inform dose escalation decisions.

In case of suspicion of a DLT, the Investigator must inform the Medical Monitor/Sponsor immediately. The DLT will be confirmed by the Medical Monitor/Sponsor and a decision must be taken by the Sponsor regarding if an *ad hoc* SRC meeting is required.

Patients who are tolerating HS-130/HS-110 will not have to discontinue dosing prematurely due to the

occurrence of DLTs in another patient in the same cohort, unless decided by the SRC. If requested by the Investigator, depending on the nature of the DLT and patient status, the SRC and the Sponsor may allow a patient to continue with study treatment at a reduced dose.

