8.1.2.4 Serious Adverse Event (SAE)

A serious adverse event is defined as any untoward medical occurrence that at any dose:

1. Results in death,
2. Is life-threatening (i.e., the patient was at risk of death at the time of the event. It does not refer to an event which hypothetically might have caused death if it was more severe),
3. Requires in-patient hospitalization or prolongation of existing hospitalization excluding that for pain management, disease staging/re-staging procedures, or catheter placement unless associated with other serious events,
4. Results in persistent or significant disability/incapacity, or
5. Is a congenital anomaly/birth defect.

Important medical events that may not result in death, be life-threatening, or require hospitalization may be considered serious adverse drug events when, based on appropriate medical judgment, they may jeopardize the patient or subject and may require medical or surgical intervention to prevent one of the outcomes listed above.

Disease Progression, or death as a result of disease progression, **are not considered to be SAEs**. However, if the progression of the underlying disease is greater than what would normally be expected as part of the natural course of the disease under study for the patient, or if the Investigator considers that there was a causal relationship between treatment with study drug or protocol design/procedures and the disease progression, then it must be reported as an SAE.

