8.1.2.8 Safety Data Review

8.1.2.8.1 Safety Review Committee

A Safety Review Committee (SRC) comprises of 3 members – one Investigator, a representative from Heat Biologics and the Medical Monitor will evaluate the data obtained at each dose level including a review of all adverse events (serious and non-serious adverse events) as they are reported by the study site. The SRC will recommend whether the dose should be escalated as per protocol, revised to a lower level or

intermediate level, halted altogether or more patients are required at the same dose level to evaluate safety. If a DLT is observed already with the first patient treated in Cohort 1, the SRC may suggest and approve dose de-escalation with at least 50% reduction of HS-130 and HS-110 (dose level -1), depending on the nature of the reaction.

Ad-hoc SRC meetings may be called for by both the SRC and Sponsor any time during the study if DLTs are observed and/or new safety data warrants immediate action to the conduct of the trial (including events defined by the Study Stopping Criteria in Section 5.5).

The conclusion of the SRC meeting will be documented in meeting minutes. The outcome of the SRC meeting will be communicated to all Investigators.

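### Read literally, the Section 5.5 bracket exempts from the automatic dosing hold even a progression death that the Investigator has reported as an SAE because study drug is considered the cause

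*Combined protocol and SAP*

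**What the plan says.** Section 5.5 (Study Stopping Criteria) lists two events that stop HS-130/HS-110 pending SRC review. The first is "Any Death (other than progressive disease) that is at least possibly related to the study agent(s". The second is "Occurrence of two or more grade 4 events that are at least possibly related to the study agent(s". The stop applies to the whole study: "During that time, no drug can be administered to any patient, until a decision is made". Section 4.5 describes 5.5 as the list of events that call for treatment to stop at once until the SRC has looked at them.

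Section 8.1.2.4 also excludes disease progression, and death from it, from the definition of an SAE. It then restores SAE status in two situations. One is progression worse than the natural course would lead one to expect. The other applies "if the Investigator considers that there was a causal relationship between treatment with study drug or protocol design/procedures and the disease progression".

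Under Section 8.1.2.7 an SAE goes to the Sponsor or its designee within 24 hours of the site becoming aware of it. Under Section 8.1.2.8.1 the SRC assesses safety one dose level at a time, and its remit is worded as "including a review of all adverse events (serious and non-serious adverse events) as they are reported by the study site". Either the SRC or the Sponsor may convene it ad hoc.

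**The concern.** Sections 5.5 and 8.1.2.4 share a default: a progression death does not count. Section 8.1.2.4 qualifies it for progression that the Investigator believes the treatment caused, and 5.5 does not. The protocol thus accepts that drug-caused progression is possible and serious enough to report urgently, yet its stopping rule, taken at its word, passes over a death from it.

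HS-130 has no previous human exposure (Section 2.4), and Section 4.1 allows treatment past progression under stated conditions. If an Investigator concludes that study drug caused a fatal progression, that conclusion bears on every patient still being dosed. After a related death from any other cause, dosing stops for everyone until the SRC decides. After this one, patients can be dosed on schedule unless someone chooses to intervene. Cycles are 14 days with a visit window of ±2 days, so a patient's next dose can fall due before an SRC decision, for which the protocol sets no deadline.

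**Working it through.** No arithmetic applies. The plan states no operating characteristic for 5.5, and the point turns on wording. The check has two parts.

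**1. What the bracket does under a literal reading**

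- The first trigger already requires relatedness, so a death judged unrelated fails it with or without the bracket.
- Section 8.1.2.2 has three attribution levels: Unrelated, Possible and Definite. An event counts as associated with the product if it is rated Possible or Definite.
- The bracket can therefore change the outcome only for progression deaths rated Possible or Definite. Those include the deaths that the causality limb of 8.1.2.4 turns into SAEs.

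**2. Following one such death through every rule that might stop dosing**

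| Rule | Effect on other patients' dosing while review is pending |
|---|---|
| 5.5, first trigger | Not met, because of the bracket |
| 5.5, second trigger | Not met by the death itself: a death is grade 5, and the trigger needs two or more grade 4 events |
| 8.1.2.4 and 8.1.2.7 | Reported as an SAE within 24 hours; no pause attached |
| 8.1.2.8.1 | SRC reviews and may recommend halting; an ad hoc meeting may be called; no pause before the recommendation |
| 6.1.2 | If the death counted as a DLT, patients tolerating treatment "will not have to discontinue dosing prematurely due to the occurrence of DLTs in another patient in the same cohort", unless the SRC decides otherwise |
| 6.1.1 | SRC review comes before escalation, and a drug-related event in the first cycle of the accelerated cohort can return the study to 3+3; both govern enrolment and dose level, not continuing doses |
| 6.2 | An Investigator may withhold drug from an individual patient; no study-wide hold |
| 4.5 | The Sponsor may terminate the study; discretionary |

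No row gives an automatic study-wide pause. Review is assured, but a pause during it depends on a decision by the SRC, the Sponsor or an Investigator.

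**The case against.** The strongest reply is that the bracket was meant for deaths from the underlying cancer. On that view, a death the Investigator attributes to study drug is a drug-related death and falls outside the bracket. This is a reasonable reading of the intent. The bracket also has a sound use. The attribution scale reserves Unrelated for events plainly unconnected with treatment, so in a refractory population an ordinary progression death may be rated Possible simply because a link cannot be excluded. Without the bracket, such deaths could stop the study repeatedly. All of this stands, and it is why the bracket should be qualified and not deleted. But the text does not state the narrower meaning, and a rule that stops dosing should not depend on inferring it.

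The second reply is that the available powers are enough. The causality judgement is made by an Investigator, an Investigator sits on the SRC, the synopsis names one study center, and the SRC may meet at any time. A prompt meeting could well precede many patients' next dose. That is fair, and it limits the consequence. It does not alter the fact that the pause is automatic for other related deaths and discretionary for this one.

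A reader might infer three stronger points that the documents do not support:

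- **That such a death would escape review.** It would not: 24-hour notification and SRC review both apply.
- **That the DLT definition would exclude the event**, since it covers only toxicity "not attributable to the active disease, disease-related processes under investigation or intercurrent illness". That conflicts with the premise of a death considered drug-caused. Section 6.1.2 presumes relatedness unless another explanation is clear and documented, so such a death within the four-week window could count as a DLT. It is enough that a DLT does not by itself pause other patients.
- **That the Sponsor deliberately exempted drug-caused progression deaths.** Nothing in the text shows this.

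**Conclusion.** The point holds in a narrow form. Read literally, the first 5.5 trigger exempts every progressive-disease death from the automatic hold, including one whose progression has been reported as an SAE because the Investigator considers study drug causal. The defect is the missing automatic pause, not missing oversight, and it may be unintended.

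Its size cannot be expressed as a probability, because the documents give no rate. The event is likely rare: over 100 patients have received HS-110 (Section 2.4), with no HS-110-related deaths reported (Section 2.6). HS-130 has no human data, so that reassurance does not extend to the combination. The study plans 13 to 30 patients. No sample size, error rate or analysis is affected.

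The conclusion assumes that sites would apply the bracket as written and that no separate charter or safety plan, outside these documents, adds a hold. The change is worth making because it is cheap and the rule protects patients in a first-in-human study. It is not a reason to regard the safety monitoring as inadequate.

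**What to change.** In the first 5.5 bullet, keep the relatedness condition and replace the bracket with an exclusion along these lines: *excluding death from progressive disease, unless the progression was reported as an SAE under Section 8.1.2.4 because the Investigator considers there was a causal relationship with study drug.*

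The SAE report on that limb is the sole test. Sites do not have to divide the Possible rating into kinds that the attribution scale does not record, and ordinary progression deaths stay outside the hold, even if rated Possible. Two other parts of 8.1.2.4 also stay outside: progression merely faster than expected, and progression attributed to protocol design or procedures. The latter is consistent with 5.5, which concerns the study agents.

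The cost is one clause in an amendment and, rarely, a short study-wide dosing pause until the SRC decides. If the narrower meaning was intended all along, the clause simply writes it down.
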